4.3 Study Setting

The study will be conducted at 9 US centers. The maximum enrollment at each individual site will be limited to 50 participants.

4.4 Subjects

Participants will be adult patients (21 years of age or above) with a BMI ≥ 30 and ≤ 40 kg/m² that meet the eligibility criteria below. All eligibility criteria must be met at the time of randomization.

4.5 Inclusion Criteria

1. Age 21-65
2. BMI ≥ 30 and ≤ 40 kg/m²
3. Willingness to comply with the substantial lifelong dietary restrictions required by the procedure
4. History of failure with non-surgical weight-loss methods
5. Willingness to follow protocol requirements, including signed informed consent, routine follow-up schedule, completing laboratory tests, and completing diet counseling
6. Residing within a reasonable distance from the investigator's office and able to travel to the investigator to complete all routine follow-up visits
7. Ability to give informed consent
8. Women of childbearing potential (i.e., not post-menopausal or surgically sterilized) must agree to use adequate birth control methods
9. ***There will be a quota for at least a) 50 patients with hypertension on one or more anti-hypertensive medication, b) 50 patients with type II diabetes mellitus on oral agents only with HgA1c ≤ 9 , and thus the cohort of 200 patients will be stratified into three groups (Obesity, Obesity HTH, Obesity DM) and block randomized. No more than 50 participants without comorbidities will be enrolled in the trial.

4.6 Exclusion Criteria

1. History of foregut or gastrointestinal (GI) surgery (except uncomplicated cholecystectomy or appendectomy)
2. Prior gastrointestinal surgery with sequelae, i.e. obstruction, and/or adhesive peritonitis or known abdominal adhesions.
3. Prior open or laparoscopic bariatric surgery.
4. Prior surgery of any kind on the esophagus, stomach or any type of hiatal hernia surgery.
5. Any inflammatory disease of the gastrointestinal tract including severe (LA Grade C or D) esophagitis, Barrett's esophagus, gastric ulceration, duodenal ulceration, cancer or specific inflammation such as Crohn's disease.
6. Potential upper gastrointestinal bleeding conditions such as esophageal or gastric varices, congenital or acquired intestinal telangiectasis, or other congenital anomalies of the gastrointestinal tract such as atresias or stenoses.
7. Gastrointestinal stromal tumors, history of premalignant gastric lesions (intestinal metaplasia), history of familial and non-familial adenomatous syndromes.
8. A gastric mass or gastric polyps > 1 cm in size.
9. A hiatal hernia > 4cm of axial displacement of the z-line above the diaphragm or severe or intractable gastro-esophageal reflux symptoms.
10. A structural abnormality in the esophagus or pharynx such as a stricture or diverticulum that could impede passage of the endoscope.
11. Achalasia or any other severe esophageal motility disorder
12. Severe coagulopathy.
13. Insulin-dependent diabetes (either Type 1 or Type 2) or a significant likelihood of requiring insulin treatment in the following 12 months or a HgbA1C \geq 9.
14. Subjects with any serious health condition unrelated to their weight that would increase the risk of endoscopy
15. Chronic abdominal pain
16. Motility disorders of the GI tract such as gross esophageal motility disorders, gastroparesis or intractable constipation
17. Hepatic insufficiency or cirrhosis
18. Use of an intragastric device prior to this study due to the increased thickness of the stomach wall preventing effective suturing.
19. Active psychological issues preventing participation in a life-style modification program as determined by a psychologist
20. Patients unwilling to participate in an established medically-supervised diet and behavior modification program, with routine medical follow-up.

21. Patients receiving daily prescribed treatment with high dose aspirin (> 80mg daily), anti-inflammatory agents, anticoagulants or other gastric irritants.
22. Patients who are unable or unwilling to take prescribed proton pump inhibitor medication
23. Patients who are pregnant or breast-feeding.
24. Subjects with Severe cardiopulmonary disease or other serious organic disease which might include known history of coronary artery disease, Myocardial infarction within the past 6 months, poorly-controlled hypertension, required use of NSAIDs
25. Subjects taking medications on specified hourly intervals that may be affected by changes to gastric emptying, such as anti-seizure or anti-arrhythmic medications
26. Subjects who are taking corticosteroids, immunosuppressants, and narcotics
27. Subjects who are taking diet pills
28. Symptomatic congestive heart failure, cardiac arrhythmia or unstable coronary artery disease.
29. Pre-existing respiratory disease such as moderate or severe chronic obstructive pulmonary disease (COPD) requiring steroids, pneumonia or cancer.
30. Diagnosis of autoimmune connective tissue disorder (e.g. lupus, erythematosus, scleroderma) or immunocompromised.
31. Specific diagnosed genetic disorder such as Prader Willi syndrome.
32. Eating disorders including night eating syndrome (NES), bulimia, binge eating disorder, or compulsive overeating
33. Known history of endocrine disorders affecting weight such as uncontrolled hypothyroidism.

5 TRIAL PROCEDURES

[figure not shown]
5.1 Informed consent

Prior to being enrolled in the trial, study participants must consent to participate after the nature, scope, and possible risks of the trial have been explained and outlined in an understandable form to them per the requirements of the IRB. The written informed consent document is provided in Appendix X. Participants are free to withdraw consent at any time.

After reading the informed consent document, the participant must sign and date the latest approved version of the informed consent form before any study procedures are performed. A copy of the signed consent document will be given to the participant, and the original signed consent form will be retained by the investigator.

5.2 Study Timeline

The study timeline is depicted in the figure below:

5.3 Screening and Eligibility Assessment

Screening will be conducted by the investigator or the co-investigator and documented on the Investigator delegated/medically qualified team member intake form (conventionally known as PI Intake Form) (Appendix A) and Screening Labs form (Appendix B). Screening must occur no more than 45 days prior to randomization.

Screening will include the following:

1. Sign informed consent form
2. Screening exam and intake by the investigator or co-investigator
3. Height, weight and BMI; waist and hip circumference; vital signs (blood pressure and pulse)
4. Dietary screening intake and approval
5. Laboratory tests (after 8 hours fasting)

- **CBC:** Hgb, Hct, WBC, MCV, platelets
- **Chemistry panel:** sodium, potassium, chloride, CO₂, BUN, creatinine, fasting glucose, insulin, SGOT/AST, SGPT/ALT, alkaline phosphatase, total bilirubin, direct bilirubin, total protein, albumin, fasting lipids profile (total cholesterol, triglyceride, LDL cholesterol, HDL cholesterol) Fe/TIBC, iron, B12, 25-Hydroxy Vitamin D, TSH, total Ghrelin level (only if available at participating institution), C-reactive protein.
- **Coag:** Pro Time or INR, PTT
- **PYY-1, GLP-1, Total Ghrelin** pending sites' availability to analyze
- **Urinalysis**
- **HgbA1C**
- **H. Pylori Breath Test.** **Patients with a positive h-pylori breath test will be treated and eradication must be confirmed with a stool antigen after treatment and prior to randomization**
- **EKG** for patients 50 years old or older
- **Urine pregnancy test** for women of child bearing potential

6. Questionnaires
7. Psychological evaluation and approval: Study psychologists will use their standard clinical evaluations for bariatric interventions.

Within one week of completion of the screening tests, the PI will review the results and determine the participant's eligibility. The center will inform the participant of their screening results within 10 days of completing testing. Any abnormal lab results will be communicated to the participant and they will be required to notify their primary care provider for any further action that may be necessary. All potential participants who qualify for randomization based on the initial screening assessments will return for a randomization visit where participants will have the chance to review any questions with the study staff, as well as a recap of the follow-up schedule, and they will then receive their randomization assignment.

5.4 Randomization

Participants will be stratified to three groups (Obesity, Obesity HTN, and Obesity DM) and will be randomly assigned to treatment or control group with a 1:1.5 allocation per a computer generated randomization using variable block randomization.

Participants will be notified of their randomization assignment on the day of the randomization visit. Participants randomized to the control group will proceed to an appointment with the dietitian for their Week 1 visit on the day of randomization. Participants randomized to the treatment group will proceed to a brief visit with the dietitian to review the post-op liquid diet, and the ESG will be scheduled within 30 days of randomization. Participants of child-bearing potential will be required to have a pregnancy test within 7 days of the scheduled ESG.

5.5 Trial Intervention

5.5.1.1.1 Control group

Participants randomized to the control group (lifestyle intervention only) in Level 1 will undergo a standard moderate intensity life-style intervention during the first 12 months of Level 1. The first dietary visit will be scheduled on the day of randomization. A low-calorie diet plan will be reviewed with each participant and will be adjusted according to each participant's needs. Participants in the control group will not undergo the liquid transitional diet as it is difficult to achieve compliance without intervention. Physical activity, including 150 minutes of aerobic exercise per week, will be encouraged and assessed for compliance during the study. Participants will have 12 follow-up visits in the 12 months of Level 1 as described in the schedule of events. Participants will receive \$100 for every 4 visits they attend consecutively in Level 1 with the ability to earn a maximum of \$300 at the end of the first 12 months of Level 1.

Control group participants who were compliant with at least 75% of visits in the first 12 months of Level 1, have not achieved $\geq 25\%$ EWL measured at the week 52 visit, or still have a BMI ≥ 30 and ≤ 40 , and have no new psychosocial contraindications as deemed by the treatment team to the procedure will cross over to receive ESG in Level 2, in addition to the standard moderate intensity lifestyle intervention program for 12 months. After crossing over into Level 2, participants will be able to earn the same remuneration as in Level 1 (\$100 for every 4 consecutive visits attended). Those who were compliant with attending 75% of the visits in Level 2 (second 12 months) will receive a bonus of \$300 at the final study visit, for a potential total of \$900 earned in the two years.

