- Improvement/reduction of hunger and desire to eat evaluated using validated self-reported ratings of appetite based on a 100-mm visual-analogue scale
- Improvement in eating behaviors evaluated using the Three Factor Eating Questionnaire (TFEQ)
- Among LS randomized group with ESG at 12 months – outcome of 24 month %EWL

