	Enrollment; Screening/ Baseline	Randomization / Week 1 visit	Weeks 4, 8	Week 12	Weeks 16, 20	Week 24 (6 month)	Weeks 30, 36, 42, 48	Week 52 (Final Year 1 visit), re-screen for crossover to ESG	Unscheduled Visit
Visit Number	-1	1	2,3	4	5,6	7	8,9,10,11,	12	
Informed consent	X								
Complete Physical Exam (CPE) by Investigator or Investigator delegated / medically qualified team member	X			X		X	X	X	X
Investigator or Investigator delegated/medically qualified team member exam		X ⁺⁺	X	X	X	X	X	X	X
EKG if (> 50 yo)	X							X	
Formal nutritional assessment	X								
Formal psychology evaluation	X								
Pregnancy test (females of childbearing potential only)	X								
Laboratory tests, H-pylori breath testing (baseline only)* *	X							X	
Questionnaires#	X			X		X		X	
Inclusion/exclusion criteria	X							X	
Endoscopy / Procedure									
Procedure Assessment Form									
GERD Questionnaire + Activity Assessment Form	X	X	X	X	X	X	X	X	
Weight, BMI/height, Waist and Hip Circumference Form	X	X	X	X	X	X	X	X	X
Vital Signs Form	X	X	X	X	X	X	X	X	X
Adverse Events Form		X	X	X	X	X	X	X	X
Medications Form##	X	X	X	X	X	X	X	X	X
Post-enrollment Nutrition / Exercise / satiety counseling and assessment		X	X	X	X	X	X	X	
Randomization to ESG vs. LS ⁺		X							
Subject Satisfaction Questionnaire (control phase)								X	

** Electrolytes, Creatinine, CBC, Iron, TIBC, B12, 25-hydroxy Vitamin D, TSH, HgA1c, fasting blood sugar and insulin, PTT, fasting lipids profile (total cholesterol, LDL, HDL, and Triglyceride), ALT, AST, ALK-P, total bilirubin, direct bilirubin, BUN, total protein, albumin, CRP, urinalysis; also include PYY-1, GLP-1 and total Ghrelin pending sites' availability to analyze

Eating disorder questionnaire + hospital anxiety and depression questionnaires (only at base-line), IWFQOL-Lite, SF36, PHQ9, Pittsburgh Sleep Quality Index (PSQI), Three factor eating questionnaire (TFEQ)

Record all medications including dose and frequency; especially diabetes and blood pressure medication.

+ LS start with the week 1 visit with no transitional diet.

++ Required only for Week 1 visit

5.6.1.1.4 Schedule of Events for Control Group, Crossover in Year 2, Level 2

[figure not shown]
TABLE 3. MERIT SCHEDULE OF EVENTS (Year 2, Level 2, Control Group, cross-over 120 patients)									
	ESG Procedure	Post-Op Phone Call	Weeks 1, 4, 8	Week 12	Weeks 16, 20	Week 24 (6 month)	Weeks 30, 36, 42, 48	Week 52 (Final Year 1 visit)	Unscheduled Visit
Visit Number	0	-	1,2,3	4	5,6	7	8,9,10,11	12	

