Informed consent for cross-over procedure									
Complete Physical Exam (CPE) by Investigator or Investigator delegated / medically qualified team member				X		X	X	X	X
Investigator or Investigator delegated/medically qualified team member exam			X	X	X	X	X	X	X
EKG if (> 50 yo)									
Pregnancy test (females of childbearing potential only)									
Laboratory tests **						X		X	
Questionnaires#				X		X		X	
Endoscopy / Procedure	X								
Procedure Assessment Form	X								
GERD Questionnaire+ Activity Assessment Form			X	X	X	X	X	X	
Weight, BMI/height, Waist and Hip Circumference Form	X		X	X	X	X	X	X	X
Vital Signs Form	X		X	X	X	X	X	X	X
Adverse Events Form	X	X	X	X	X	X	X	X	X
Medications Form##	X	X	X	X	X	X	X	X	X
Post-enrollment Nutrition / Exercise/ satiety counseling and assessment			X	X	X	X	X	X	
Subject Satisfaction Questionnaire (treatment phase)								X	

** Electrolytes, Creatinine, CBC, Iron, TIBC, B12, 25-hydroxy Vitamin D, TSH, HgA1c, fasting blood sugar and insulin, PTT, fasting lipids profile (total cholesterol, LDL, HDL, and Triglyceride), ALT, AST, ALK-P, total bilirubin, direct bilirubin, BUN, total protein, albumin, CRP, urinalysis; also include PYY-1, GLP-1 and total Ghrelin pending sites' availability to analyze

Eating disorder questionnaire+ hospital anxiety and depression questionnaires (only at baseline), IWFQOL-Lite, SF36, PHQ9, Pittsburgh Sleep Quality Index (PSQI), Three factor eating questionnaire (TFEQ)

Record all medications including dose and frequency; especially diabetes and blood pressure medication.

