7 STATISTICAL ANALYSIS

7.1 Power and Sample Size

The primary endpoint for power and sample size is %EWL at 12 months. The null hypothesis is no difference in mean %EWL between ESG and LS randomized arms ($H_0: \mu_t = \mu_c$ where μ_t is the average %EWL in the ESG group and μ_c is average %EWL in the LS group). We will perform a two-sided hypothesis test at alpha level 0.05 (alternative hypothesis $H_a: \mu_t \neq \mu_c$) Based on the published literature with the ESG technique a conservative presumption is 25% EWL in the ESG arm with a standard deviation (SD) of 30% at 12 months compared to 10% EWL on LS alone with SD of 5%. We plan a 1:1.5 randomization scheme that allocates 3 patients to LS for every 2 to ESG at the time of randomization. Based on a two-sample t-test with unequal variances and two-sided alpha=0.05, we would have 80% power to detect a difference of 15% in average %EWL between groups with 34 patients allocated to ESG and 51 randomized to LS. 90% power would require group sizes of 45 and 68, respectively. To allow for dropout, and more importantly, to power exploratory aims for obesity comorbidity subgroups, we propose the initial randomization of 200 patients – 80 to ESG and 120 to LS.

120 subjects are initially randomized to LS in level 1. Of these, we anticipate up to 20% will achieve a successful decrease of $\geq 25\%$ in %EWL through LS alone at 12 months. Further, we anticipate up to 20% may be lost to follow up or drop out prior to 12 month follow up. Thus, we anticipate at least 77 ($120 * 0.8 * 0.8$) subjects to continue to level 2 and be offered ESG. We will test the one-sample hypothesis (non-randomized) that of those offered ESG at 12 months, average change in %EWL will be at least 10%. Based on a one-sample t-test with two-sided alpha=0.05 and standard deviation at 24 months of 30%, 70 subjects completing ESG would have 98% power to detect an effect of 25% reduction in %EWL.

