7.2.2 Secondary Aims

Continuous secondary outcomes, including change in systolic and diastolic blood pressure and change in HbA1c, QOL questionnaires such as the SF-36, PHQ-9, and eating behavior scores will be compared between treatment arms using ANCOVA with adjustment for the same variables specified in the primary analysis.

Binary outcomes, including proportion with $\geq 25\%$ reduction in %EWL and incidence of esophagitis will be compared between treatment arms by Pearson Chi-square test.

Among patients randomized to the treatment ESG group, the association between the durability of plication at repeat endoscopy (score ≥ 1 on EGD grading system) and number of sutures required for re-tightening with change in EWL from 12 months to 24 months will be assessed using linear regression with adjustment for BMI, %EWL between randomization and 12 month follow up, HTN status, and DM status. This is an observational comparison.

Among patients randomized to the control LS arm, the percent EWL from the 12 month assessment to the 24 month assessment will be measured. This percentage will be compared to percent EWL in the same group with lifestyle intervention only in the first 12 months using a one sample t-test.

Among all subjects, %EWL will be compared at 24 months between initial and delayed ESG. However, this is not considered a comparison of randomized arms as follow up is not continued for patients with $\geq 25\%$ EWL from LS at 12 months.

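### The crossover rule in 5.5.1.1.1 uses *or*, so a lifestyle responder still at BMI 30-40 qualifies for ESG, while 7.2.2 ends follow-up of that same patient

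*Combined protocol and SAP*

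**What the plan says.** Section 5.5.1.1.1 sets the rule for controls at the end of Level 1. They must have attended at least 75% of visits and have no new psychosocial contraindication. Between these two conditions stands the disputed one: not having reached 25% "EWL measured at the week 52 visit, or still have a BMI" between 30 and 40. Those who qualify will cross over to ESG.

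Three other places bear on the same patients:

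- Section 7.2.2, explaining why the 24-month comparison of initial and delayed ESG is not randomized, states that "follow up is not continued for patients with" 25% EWL or more from lifestyle at 12 months. It makes no exception for BMI.
- Section 7.1 takes 120 controls, removes up to 20% as lifestyle successes and up to 20% as dropouts, and concludes: "Thus, we anticipate at least 77" "subjects to continue to level 2 and be offered ESG".
- The control-group schedule in 5.6 labels week 52 as "re-screen for crossover to ESG" and marks the inclusion/exclusion row there. The Level 2 schedule has a row headed "Informed consent for cross-over procedure".

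The Level 2 analyses that use these patients include the 24-month %EWL endpoint in 4.2.1 ("Among LS randomized group with ESG at 12 months"), the pooled blood-pressure and HbA1c endpoints in 4.2.1, and a one-sample test in 7.2.2 of second-year %EWL in the control arm. Of that last result, the plan says: "This percentage will be compared to percent EWL in the same group with lifestyle intervention only in the first 12 months".

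**The concern.** A control with 25% EWL or more and BMI still 30-40 receives two incompatible instructions: cross over to ESG under 5.5.1.1.1, or leave follow-up under 7.2.2. The section that sites act on is 5.5.1.1.1, and nine centers could resolve the conflict differently.

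The rule decides whether someone who succeeded on lifestyle alone is offered an elective procedure under general anesthesia with intubation. Section 5.5.1.1.2 spares an ESG-arm patient with more than 25% EWL a repeat endoscopy, yet for a control the same success would not rule out a first ESG.

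The rule also fixes the population of the crossover %EWL endpoint, the case mix of the pooled endpoints, and the 24-month initial-versus-delayed comparison. In the 7.2.2 test the comparator is first-year %EWL in the same patients, so the crossover rule selects directly on that comparator.

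**Working it through.** **The plan's own figures.** The count in 7.1 is 120 × 0.8 × 0.8 = 76.8, or 77. The one-sample t-test (25 against 10, SD 30, two-sided 0.05) has 98.5% power at n = 70. Both stated figures reproduce.

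**Can both conditions hold at once?** Section 2.3 bases %EWL on an ideal BMI of 25. With baseline BMI B, BMI at exactly 25% EWL is 25 + 0.75 × (B − 25). Setting this at 30 or more gives B ≥ 25 + 5/0.75 = 31.67. A patient starting at 35 ends at 32.5; one starting at 40 ends at 36.25. Most of the 30-40 entry range is therefore open to the conflict.

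**Does other text settle it?** Section 4.1 limits crossover to eligible controls, which points back to this rule. The week-52 re-screen applies the inclusion and exclusion criteria in 4.5 and 4.6, and none of them refers to EWL. A consent row does not define eligibility.

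**How many people?** Retained controls: 120 × 0.8 = 96. Responders at the 20% ceiling: 96 × 0.2 = 19.2. The number affected is thus 0 to 19, before the 75% attendance condition. Within that range it depends on the spread of lifestyle %EWL:

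- Section 7.1 assumes a lifestyle mean of 10 and SD of 5. The one-sided Chebyshev bound gives P(X ≥ 25) ≤ 25/(25 + 225) = 0.10 for any distribution, so at most 9.6 of 96 expected. If %EWL is normal, P(Z ≥ 3) = 0.00135, or 0.13 of 96.
- A normal distribution with mean 10 gives 20% responders only if its SD is 17.8 (back-solved; not in the plan).

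The table simulates 2,000,000 lifestyle patients with normal %EWL, mean 10, scaled to 96. Ranges cover four assumed baseline BMI shapes: uniform 30-40, and truncated normal with mean 33, 35 or 37 and SD 2.5. Attendance and psychosocial conditions are not applied.

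| %EWL SD | Level 2 size, printed *or* (no re-screen) | Level 2 size, both conditions required | Mean first-year %EWL of crossers, *or* | Mean first-year %EWL, <25% EWL only |
|---|---|---|---|---|
| 5 | 96.0 | 90.1 to 95.5 | 10.0 | 10.0 |
| 10 | 94.2 to 95.8 | 83.5 to 88.0 | 9.6 to 10.0 | 8.6 |
| 17.8 | 88.4 to 94.5 | 69.3 to 73.5 | 7.5 to 9.4 | 3.8 |

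At SD 17.8, subtracting the 76.8 non-responders from the *or* pool gives the responders let in: 88.4 − 76.8 = 11.6 to 94.5 − 76.8 = 17.7, or about 12 to 18. Assuming instead uniform baseline BMI and various uniform spreads of responder EWL, 44% to 83% of responders stay at BMI 30 or more, which is 8 to 16 of 19.2.

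**Effect on power.** Under *or* the pool is 77 to 96, so the floor holds. Power is 99.1% at n = 77 and 99.8% at n = 96. If both conditions are required and the pool falls to 69, power is 98.4% provided all complete ESG.

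**The case against.** The strongest reply has four parts.

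1. *The only direct conflict is with one explanatory sentence in 7.2.2.* The count in 7.1 is a floor, and a floor that assumes no responder crosses over is compatible with some doing so. This stands as far as the figure goes: 77 is not falsified. But 7.1 reaches it by removing responders from those offered ESG, which is a different rule from the one in 5.5.1.1.1.

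2. *Week 52 already re-checks BMI.* BMI 30-40 is an inclusion criterion, so the re-screen probably enforces it. This is a fair reading and would reduce the *or* pool at SD 17.8 to 83 to 89. It does not remove the conflict, because a responder at BMI 30-40 passes the re-screen.

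3. *The comparator argument does not favor the stricter rule.* Requiring <25% EWL moves mean first-year %EWL further from the unselected lifestyle mean of 10 (to 3.8 at SD 17.8) than *or* does (7.5 to 9.4). This is correct. The comparison shows that the choice of rule matters to the test, not that *or* is the worse choice.

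4. *The size is uncertain and the harm limited.* On the SD in 7.1 almost nobody is affected. Those who are affected still have obesity, are re-screened and have a crossover consent step. Whether 25% EWL should bar them is the sponsor's decision. All true, but 7.1 itself plans for up to 20% responders, so the crossover rule has to say what happens to them.

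**Conclusion.** The concern holds. As printed, 5.5.1.1.1 sends to ESG a group that 7.2.2 drops from follow-up and 7.1 leaves out of those offered ESG. The authors probably meant *and*, but nothing in the current text says so. The contradiction follows from the wording and the definition of %EWL; it needs no distributional assumption.

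Its size does need one. The affected number lies between 0 and 19 of 96: about 12 to 18 at the 20% responder ceiling under the assumed BMI shapes, and about 0.1 with SD 5 and normality. The effect on the 7.2.2 comparator varies likewise, from none at SD 5 to a first-year mean of 3.8 against 7.5 to 9.4 at SD 17.8.

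The randomized 12-month primary analysis, the floor of 77 under *or* and the 98% power at n = 70 are not undermined. The point should be corrected because it governs who receives a procedure and who enters the Level 2 analyses.

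**What to change.** In 5.5.1.1.1, make <25% EWL at week 52 a required condition for crossover, and state whether BMI 30-40 is also required; if it is, replace *or* with *and*. The BMI statement is needed in any case: a control starting at BMI 31 with 20% EWL ends at 31 − 0.20 × 6 = 29.8, which satisfies the printed rule but not the BMI inclusion criterion.

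If BMI 30-40 is also required, note in 7.1 that the floor could fall somewhat below 77: about 69 to 74 at both 20% ceilings under the assumed BMI shapes, and higher if fewer controls respond. Do not present 77 as a maximum.

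If the sponsor instead wants responders at BMI 30-40 to cross over, amend the follow-up statement in 7.2.2 and the responder exclusion in 7.1. Report these patients separately in the Level 2 analyses, including the comparison of first-year and second-year %EWL.

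The cost is one connector and one clarifying sentence in 5.5.1.1.1, plus either a note in 7.1 or one amended sentence each in 7.1 and 7.2.2. The sample size does not change.
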